### **Data Analysis & Statistical Considerations**

Sample Size. Study goals are intervention protocol and mobile app development, feasibility, acceptability, and initial outcome patterns suggesting efficacy of a psychosocial intervention. We have used sample sizes from 15-40 to test feasibility, acceptability, and outcome patterns suggesting efficacy of a novel intervention or intervention delivery, successfully publishing these trials and using data to secure larger funding.

Aim 1 Analyses. Focus groups will be audio-recorded and transcribed. Recordings and transcripts will be reviewed by Drs. [name] and [name]. These reviews will refine the discussion guide for the subsequent focus group. Data analyses will be based on a grounded theory approach, which has been used by [name] in development of other psychosocial interventions for patients with cancer.

Aim 2 Analyses. Feasibility will be assessed by examining accrual, adherence, and attrition. Accrual will be indicated by meeting the recruitment goal of 40 participants in 12 months. Descriptive statistics will be used to report the number of HCT patients screened and determine rates of non-eligibility and refusal. Adherence will be indicated by calculating the proportion successfully completing all intervention sessions within the HCT Symptoms and Steps arm and the proportion completing post-treatment assessments within each arm. 80% completed intervention sessions and 80% completed assessments will serve as our feasibility benchmark. If less than 40% of participants complete all intervention sessions and assessments, HCT Symptoms and Steps will not be considered feasible. Attrition will be indicated by 80% of consented participants completing the study protocol (i.e., remain enrolled). Acceptability will be indicated by 80% of patients reporting satisfaction with HCT Symptoms and Steps (M=7) on the CSQ.

Aim 3 Analyses. Between-group effect sizes will be used to evaluate treatment effects on physical disability, as well as pain, fatigue, psychological distress, physical activity, and self-efficacy for symptom management. Between-group effect sizes will provide an index of relative change for HCT Symptoms and Steps participants vs. HCT Education participants. Because small samples can differ on pretest scores, effect sizes will be calculated by first creating change scores for each person. The between-group effect size will then be calculated by subtracting the average HCT Education group change score from the average HCT Symptoms and Steps change score, and dividing this difference by the standard deviation of the pooled treatment/control group's change score. This study is not designed to make conclusions about efficacy without further study.

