inpatients, have weeks of intensive outpatient care, and then return home often many miles from the hospital. HCT patients return home with compromised immune functioning, low vigor, and restriction on normal activities (e.g., driving, cooking, yard work, church) that could increase infection risk or compromise safety. HCT patients report feeling socially isolated and disconnected from their medical team. HCT patients experience these challenges during a critical time of transition from hospitalization to home. Mobile health (mHealth) technologies can improve and extend intervention strategies during this time of transition. A protocol that uses mHealth technology for delivery may be particularly beneficial for HCT patients as it allows the medical team to provide care to the patient in his /her home. The patient remains connected to the medical team during an important time of transition, which can increase continuity of care and access to treatment, and decrease patient burden.

We aim to develop and test a combined coping skills training and activity coaching protocol that: first, is feasible and acceptable, and second, improves physical disability, as well as pain, fatigue, distress, and physical activity in HCT patients. We have used the NIH Treatment Development Stage Model to inform the research activities and design. This study focuses on development (i.e., focus groups, user testing) and a small pilot trial (Stage I), with emphasis on the mHealth component and mobile app. Data gathered from research activities will inform protocol modification and study results will be used to prepare for Stage II (efficacy trial). As described in *Preliminary Studies*, the proposed interdisciplinary research team is uniquely positioned to develop and test a coping skills training for symptom management and activity coaching protocol.

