Randomized Controlled Trial. We will use a small RCT to assess the feasibility, acceptability, and outcome patterns suggesting efficacy of a HCT Coping Skills Training for Symptom Management and Daily Steps (HCT Symptoms and Steps) protocol. This study will be conducted in the ABMT Clinic with 40 HCT patients. Following consent (consent process detailed below), participants will be randomly assigned in equal allocation to one of two conditions: 1) HCT Symptoms and Steps or 2) HCT Education. HCT Symptoms and Steps will provide patients with cognitive behavioral coping skills training and activity coaching sessions to enhance their ability to manage symptoms that interfere with activity. All participants will receive a wireless activity tracker (Fitbit) to track steps; Fitbits will not be returned, participants will keep their Fitbit. All participants who do not have a smart phone will be lent one (iPhone) equipped with Internet access to access the mHealth features: video-conferencing, coping skill content, activity tracker syncing, daily symptoms assessment, and personalized feedback (via push notification) based on symptom and step data. HCT Education will only have access to activity tracker syncing and daily symptoms assessment. HCT education participants will be encouraged to download the Transplant (HCT) Guidelines mobile app that is free of charge. The Transplant Guidelines app is developed by the National Marrow Donor Program and designed for HCT patients with a focus on treatment guidelines for patients before and after transplant. The Transplant Guidelines App provides recommended annual check-up guidelines and timing and contains helpful information, checklists and reminders for patients who have had a blood or marrow transplant. App content also includes cancer education, information about health and well-being, cancer treatment guidelines specific to HCT patients, and what to expect at follow-up visits. App features allow participants to use a GvHD symptom checker to help identify early signs of GvHD and make notes, e-mail guidelines and symptom checker results to self, and set reminders for appointments, medications, and exercise. All participants will complete 2 assessments: pretreatment and post-treatment. We will recruit 10 patients per quarter (3-4/month) to complete the recruitment goal of 40. Participants will receive \$20 for completing each assessment. Th erapist Training. Coping skills training sessions will be delivered by a doctoral level psychologist with experience delivering cognitive behavioral interventions. Activity coaching sessions will be delivered by an OT with expertise working with HCT patients. Treatment strategies will be taught through didactic instruction, audio-/video-recorded illustration of techniques, and role-play. Procedures to Ensure Consistency of Treatment. To ensure consistency with the intervention protocol: 1) therapists will follow a treatment manual, 2) weekly supervision will occur, 3) sessions will be audio-recorded and reviewed during supervision and feedback provided, and 4) ratings of treatment adherence and competence will be conducted.

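### Aim 3 uses change scores because the arms may differ at pretest, but they cancel such a difference only if the post-on-pre slope is 1; adjusting for the pretest score does so with the same data

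*Combined protocol and SAP*

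**What the plan says.** The Aim 3 Analyses paragraph (Data Analysis & Statistical Considerations) starts from the risk that arms of this size will not be alike at the outset: "Because small samples can differ on pretest scores, effect sizes will be calculated by first creating change scores for each person". The numerator is obtained by "subtracting the average HCT Education group change score from the average HCT Symptoms and Steps change score", and the effect size by "dividing this difference by the standard deviation of the pooled treatment/control group's change score". I read that divisor as the pooled within-arm SD of change. The same recipe serves every Aim 3 outcome. The paragraph ends with a caveat: "This study is not designed to make conclusions about efficacy without further study".

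The Randomized Controlled Trial paragraph gives 40 patients in equal allocation and two measurement times: "All participants will complete 2 assessments: pretreatment and post-treatment".

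Neither a baseline-adjusted comparison nor a confidence interval for an Aim 3 effect size is planned anywhere. No SD or pre-post correlation is stated for any outcome.

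**The concern.** The method chosen does not match the reason given for it. A change score fixes the slope of post on pre at 1. If the true slope is below 1, an arm that starts worse by chance will on average appear to improve more, even with no treatment effect. The imbalance is then carried into the effect size with its sign reversed.

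A second point concerns the scale. Dividing by the SD of change makes the effect size depend on each measure's pre-post correlation. H3 (Purpose of the Study, Aim 3) looks for a pattern across measures, and part of any such pattern could reflect differing correlations.

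No decision rule uses these effect sizes. However, Background & Significance says the study's results will help prepare the Stage II efficacy trial. An estimate that carries a chance imbalance, has no interval and has a measure-dependent scale is a weaker planning input than the same two assessments can give.

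**Working it through.** There is no plan figure to reproduce. The sample size rests on precedent (earlier trials of 15 to 40), with no alpha, power, SD or correlation.

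**Inputs from the documents.** 40 patients in equal allocation give n = 20 per arm. The Aim 2 benchmark ("80% completed intervention sessions and 80% completed assessments will serve as our feasibility benchmark") gives 0.80 x 20 = 16 per arm as a lower case.

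**Assumptions.** Pre-post correlation r = 0.3, 0.5, 0.7. SD ratio k = SDpost/SDpre = 1, with 0.8 and 1.3 as sensitivity cases. The unit is the baseline SD. The slope is b = r x k.

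**1. Size of the chance imbalance d0 (intervention minus education).** Its SD is sqrt(2/n).
- At n = 20: SD 0.316, mean absolute size 0.252, and a 11.4% chance of exceeding 0.5 SD in either direction on a given outcome.
- At n = 16: 0.354, 0.282 and 15.7%.
- H3 lists seven measures, so the chance that at least one exceeds 0.5 SD at n = 20 is at most 1 - 0.886^7 = 57%. It is lower if the measures are correlated.

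**2. Carry-over given d0.**
- Difference in change: expected value = effect - (1 - b) x d0.
- Post score regressed on arm and pretest: expected value = effect, under a common linear slope.

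In simulation with no true effect (40,000 trials per setting, n = 20), the slope of the change-score difference on d0 was -0.70, -0.50 and -0.31 at r = 0.3, 0.5 and 0.7. For the adjusted estimate it was within 0.006 of zero. Averaged over all simulated trials, both estimators were centred on zero.

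**3. Precision.**
- Var(change) = (2/n)(1 + k² - 2rk).
- Var(adjusted) = (2/n) k² (1 - r²)(N - 3)/(N - 4), with N = 2n. The last factor is the small-sample cost of estimating the slope: 37/36 = 1.028 at n = 20 and 29/28 = 1.036 at n = 16.
- Example at n = 20, r = 0.5, k = 1: 0.100 for change, 0.1 x 0.75 x 1.028 = 0.0771 adjusted, ratio 0.77.
- 95% half-widths use t on 38 degrees of freedom for change and 37 for adjusted.

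Results at n = 20, k = 1:

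| r | Shift at d0 = 0.25 | Shift at d0 = 0.5 | Variance ratio, adjusted/change | 95% half-width, change | 95% half-width, adjusted |
|---|---|---|---|---|---|
| 0.3 | 0.18 | 0.35 | 0.67 | 0.76 | 0.62 |
| 0.5 | 0.13 | 0.25 | 0.77 | 0.64 | 0.56 |
| 0.7 | 0.08 | 0.15 | 0.87 | 0.50 | 0.46 |

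Shifts are absolute sizes. Dividing 40 by the variance ratio, adjustment on 40 patients has the precision of change scores on about 60, 52 and 46. At n = 16 the half-widths are 0.85, 0.72, 0.56 (change) and 0.70, 0.64, 0.53 (adjusted).

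**4. Sensitivity to equal SDs (n = 20; r = 0.3, 0.5, 0.7).**
- k = 0.8: variance ratios 0.52, 0.59, 0.65.
- k = 1.3: variance ratios 0.83, 0.94, 1.02. The slope is 0.39, 0.65, 0.91, so the shift at d0 = 0.5 is 0.31, 0.18, 0.05.
- k = 1, r = 0.9: variance ratio 0.98.
- At b = 1 exactly, both variances are (2/n)(k² - 1) before the small-sample factor. The cost of adjusting is then 2.8% of variance at n = 20 and 3.6% at n = 16.

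**5. Scale.** With k = 1 the SD of change is sqrt(2(1 - r)). A true effect of 0.40 baseline SD is reported as 0.40/1.183 = 0.34, 0.40/1.000 = 0.40 or 0.40/0.775 = 0.52 at r = 0.3, 0.5, 0.7.

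**The case against.** The strongest reply is that this is a feasibility pilot which disclaims efficacy conclusions, and its benchmarks concern accrual, adherence, attrition and satisfaction. The documents do not say that the Aim 3 effect size will set the Stage II sample size; that use is inferred. The estimator is unbiased over randomisation. At the average imbalance, the shift is only about 15% to 23% of the change-score half-width (0.08/0.50 to 0.18/0.76), and the intervals stay wide after adjustment. This stands, and it limits the weight of the point.

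Change scores also adjust in part. Comparing post scores alone would carry b x d0. At b = 0.7 and d0 = 0.5 that is 0.35, against 0.15 in absolute size for change scores. The two are equal at b = 0.5, and change scores do worse only below that. This is correct, but part removal is still not removal.

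Regression removes the shift only if one linear slope fits both arms. Autologous patients may consent before transplant or up to 3 months after it, and allogeneic patients within 1 month after, so a single slope is an assumption. That is fair. The same mix of recovery stages makes a slope of exactly 1, which change scores need, no easier to presume.

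Finally, the SD of change is a coherent divisor for an index of relative change. A baseline SD is not a perfect common scale either, since entry depends on pain, fatigue and distress ratings. The divisor is therefore secondary and the team's to choose.

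**Conclusion.** The concern holds. Change scores do not deliver what the plan gives as the reason for using them unless the slope is 1, and adjustment for the pretest score does so under a common linear slope. With r = 0.3 to 0.7 and equal SDs, both assumed, an imbalance of 0.5 SD shifts the reported difference by 0.15 to 0.35 SD, and change scores give up 13% to 33% of variance at 20 per arm. The size in this trial is unknown because the documents give neither r nor the SD ratio, and the gain shrinks to nothing as the slope nears 1. The algebra is certain; the magnitude is conditional. It is a worthwhile correction to a descriptive analysis and does not threaten the feasibility aims.

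**What to change.** Replace the effect-size recipe in the Aim 3 Analyses paragraph with wording such as: *For each outcome, the post-treatment score will be regressed on arm and on the pre-treatment score of the same measure. The adjusted between-group difference will be reported with a 95% confidence interval, in raw units and divided by an SD named in advance (for example the pooled baseline SD), of the same kind for all measures.*

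The change-score effect size may remain as a descriptive column. Reporting each measure's pre-post correlation would help Stage II planning. Keep the sentence disclaiming efficacy conclusions.

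The cost is two sentences, a few lines of code and one residual degree of freedom (37 instead of 38 with 40 patients). No new data are needed, since a change score already requires both values. Missing values, for example from the optional 6-minute walk test or the temporary suspension of supplied activity trackers, limit both methods alike.

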#### **Data & Safety Monitoring**

Summarize safety concerns, and describe the methods to monitor research subjects and their data to
ensure their safety, including who will monitor the data, and the frequency of such monitoring. If a
data monitoring committee will be used, describe its operation, including stopping rules and frequency
of review, and if it is independent of the sponsor (per 45 CFR 46.111(a) (6)).

### **Data & Safety Monitoring**

This trial carries minimal risk. There are not physical or side effects involved in taking part in this study. The protocol does not use an investigational drug, procedure, or device. Regardless, all adverse events, serious and non-serious, will be fully documented in the appropriate adverse event form approved by the Duke University Medical Center IRB. For each event, the investigator will provide the onset, duration, intensity, treatment required, outcome, and action taken. Any serious or significant study-related adverse event, whether or not the investigational protocol has been administered, will be reported promptly to the IRB. All patients in the study will continue their usual care during the course of the study, thus their doctors will provide monitoring of the patients' overall medical status. All research personnel who have direct contact with patients will be trained to observe and report any

adverse events to the principal investigator. The principal investigator will report any adverse events to the institutional review board at Duke University and to the NIH. An adverse event is defined as any untoward medical occurrence during the clinical investigation that has a causal relationship to the study protocol. A serious adverse event is defined as any event which results in death, is immediately life threatening, results in persistent or significant disability/incapacity, patient hospitalization, or is serious for any other reason representing significant hazard. All adverse events will be reported to Duke's IRB in real time. All data will be stored on a secure server with multiple backups created regularly. The data manager, [name], and the co-investigator, [name], will monitor the data on a monthly basis.

All interactions with study participants will be under the direction of a Licensed Clinical Psychologist (Drs. [name] [PI] and [name] [Co-I]). Interventionists in this trial will have experience with distressed patients with chronic disease. They will be trained, specifically in the context of this trial, to monitor for any signs that participants are experiencing high levels of physical or emotional distress that need to be addressed outside the context of this trial. If this is determined to be the case, the PI will work directly with the participant to move forward in a way that is in the best interest of the patient. No participant will be kept in the trial if they are experiencing increased or extreme distress. Interventionists in this trial will be carefully trained to monitor participants' psychologist status and report to the Pl. [name] (PI) will be contacted when emotional distress is identified in a participant. [name] works directly with the Cancer Patient Support Program at Duke Cancer Institute as a practicing licensed clinical psychologist and as a supervisor to psychology trainees (i. e., advanced graduate students, clinical psychology interns); she is integrated into the psychosocial care program at the cancer center and has experience referring cancer patients who are distressed to appropriate psychosocial or psychiatric care within this large team of mental health professionals. She will use the same resources when making referrals for distress participants in this study.

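### The distress rule ends trial participation, not only sessions, so post-treatment scores for distress, an Aim 3 outcome, may be lost for the participants who worsen (minor)

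*Combined protocol and SAP*

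**What the plan says.** Data & Safety Monitoring has interventionists watch for high levels of physical or emotional distress. When such distress is found, "the PI will work directly with the participant to move forward in a way that is in the best interest of the patient". The next step is categorical: "No participant will be kept in the trial if they are experiencing increased or extreme distress". The sentence speaks of the trial, not of the sessions, and it covers distress that has merely increased.

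The Randomized Controlled Trial paragraph fixes the measurement schedule: "All participants will complete 2 assessments: pretreatment and post-treatment". Aim 3 Analyses lists the outcomes as "physical disability, as well as pain, fatigue, psychological distress, physical activity, and self-efficacy for symptom management" and says that "effect sizes will be calculated by first creating change scores for each person". It names no analysis set and no method for missing scores.

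Aim 2 Analyses judges attrition by whether consented participants remain enrolled, and reports post-treatment assessment completion within each arm. Its benchmark reads: "80% completed intervention sessions and 80% completed assessments will serve as our feasibility benchmark".

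**The concern.** The criterion for leaving the trial overlaps with an outcome that the trial measures. A change score needs the post-treatment value. Someone removed between the two assessments has no interim outcome assessment to stand in for it. The app's daily symptoms assessment runs in both arms, but the plan does not make it a source for the Aim 3 distress score.

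If removal picks out people who are getting worse, the remaining participants look better than the randomised group. That matters for the between-group effect size and for tolerability, because hidden worsening under an intervention aimed at distress is something a later efficacy trial would want to know. Any tilt between arms depends on whether distress is found equally often in both. The monitors named for distress are interventionists, and sessions are described only for HCT Symptoms and Steps.

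**Working it through.** The plan gives no figure on this point, so there is none to reproduce. The check asks how large the effect could be.

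**Inputs from the plan.** 40 patients in equal allocation give 20 per arm. The Aim 3 effect size is d = (mean change in Symptoms and Steps − mean change in Education) / pooled SD of change; negative d favours the intervention. The 80% assessment benchmark gives 0.80 × 20 = 16, so an arm can lose at most 20 − 16 = 4 and still meet it, with no losses for other reasons.

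**Assumptions, none from the plan.** Distress at baseline, mid-course and post-treatment is normal with SD 1. Correlations (baseline–mid / mid–post / baseline–post) are 0.5/0.5/0.5, 0.6/0.7/0.5 or 0.6/0.8/0.5. A participant is removed once mid-course worsening exceeds 1 or 1.5 SD. Detection is complete in the intervention arm, and either complete or half as good in the control arm. Removed participants have no post-treatment score. Results come from simulated trials of 20 per arm.

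**Sampling noise.** With complete data the SD of d is about √(2/20) = 0.32. In the simulations it is about 0.33 to 0.36.

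**Ceiling by formula.** Suppose removal picked exactly the people whose final change exceeds c SD. The mean change of those left is −φ(c)/Φ(c).
- c = 1: −0.242/0.841 = −0.29, with 0.159 × 20 = 3.2 removed per arm.
- c = 1.5: −0.130/0.933 = −0.14, with 0.067 × 20 = 1.3 removed per arm.

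With no true effect and the same removal in both arms, these shifts cancel and d = 0. With removal in the intervention arm only, d is −0.32 (c = 1) or −0.15 (c = 1.5). Removal acts on mid-course information, so real shifts would be smaller.

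**Removal on mid-course change, equal detection.**

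| Threshold | Full-data d −0.31 | Full-data d 0 | Full-data d +0.31 |
|---|---|---|---|
| 1 SD | −0.25 to −0.27 | 0 | +0.23 to +0.26 (flagged) |
| 1.5 SD | about −0.28 | 0 | +0.26 to +0.27 |

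The attenuation is 0.31 − 0.27 = 0.04 to 0.31 − 0.25 = 0.06 for a benefit at 1 SD, and about 0.03 to 0.05 at 1.5 SD. If only half the effect is present at mid-course, it falls to 0.31 − 0.29 = 0.02. The top of the range, 0.31 − 0.23 = 0.08, comes only from the flagged cell. There the intervention arm loses on average 4.3 to about 5 of 20, more than the 4 that the benchmark allows.

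**Half detection in the control arm, no true effect.** The shift in d is about −0.08 to −0.14 at 1 SD and −0.03 to −0.06 at 1.5 SD. These ranges cover thresholds scaled either to the SD of the score or to the SD of mid-course change. At 1 SD the intervention arm loses about 2.6 to 3.2 of 20, within the limit of 4.

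**Removal on distress level instead.** Taking the 1 to 4 most distressed from the intervention arm only, with no true effect, moves d by 0 to −0.07. Taking the 1 to 4 with the largest mid-course change moves it by −0.05 to −0.28. The share of the intervention arm seen to worsen by more than 0.5 SD, truly 31%, is 30–31% under level-based removal. Under change-based removal it is about 22–25% (1 SD) or 28% (1.5 SD).

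**The case against.** The rule sits in a clinical safety process. The monitoring trigger speaks of high levels, and extreme distress is also a level; under that reading almost nothing is lost. It covers physical as well as emotional distress and rests on clinical judgement, with no score or time point named. Both features loosen the link between removal and the Aim 3 score, and removals may be few. This stands. The word *increased* does admit a reading based on change, so the text is ambiguous rather than safe.

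The loss of scores is inferred from silence. Nothing visible forbids a final questionnaire, and the Consent Process section points to a form outside our copy. A reader might infer that these scores will certainly be lost; the documents support only that they may be.

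A reader might also infer that the rule favours the intervention. The documents do not establish unequal detection. "All research personnel who have direct contact with patients will be trained to observe and report" adverse events, the PI is contacted about distress in any participant, and both arms complete the daily symptoms assessment.

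A third tempting reading is that the rule would conceal a true harm. The simulated cases showing this most strongly use the 1 SD threshold, where the intervention arm exceeds 4 losses on average, so they carry no weight here.

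Finally, assessment completion by arm is already planned, so a difference in losses would show. The reason for it would not.

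**Conclusion.** The point holds in a limited form and is minor. As worded, the rule makes leaving the trial depend on something the trial measures, and no visible text protects the post-treatment score.

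The size is conditional on removal following worsening and on the score not being collected afterwards. Given both, worsening is understated in each affected arm, and the between-arm effects are those in the tables and ranges above. All are well below one sampling SD of d. They are systematic, but they rest on thresholds, correlations and detection rates that the documents do not supply. If removal follows level, or clinical judgement and physical distress dilute the link, the effect is small or near zero.

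The consequence is limited further because distress is one of several exploratory effect sizes in a 40-patient pilot, and Aim 3 Analyses disclaims conclusions about efficacy.

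**What to change.** In Data & Safety Monitoring, separate stopping the intervention from leaving the study. Suggested wording: *Increased or extreme distress in either arm, in the PI's judgement, stops the study intervention and triggers referral. The participant is still invited, if willing and clinically appropriate, to complete the scheduled post-treatment questionnaires.*

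In Aim 3 Analyses, add that returned scores are analysed by assigned arm. Alongside the by-arm assessment completion in Aim 2 Analyses, report distress withdrawals by arm, which adds the reason for loss.

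No numeric trigger is needed, and the safety action is unchanged. The questionnaires and the $20 payment per assessment are already planned. The cost is a few sentences and a small consent and IRB wording change.

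The downsides are modest. Some participants will decline, so recovery is partial. For illustration, with 2 or 4 one-sided removals on mid-course change and correlations 0.6/0.7/0.5, recovering half moves d from −0.13 or −0.24 to −0.06 or −0.11. That assumes the recovered score equals the one that would have been seen without removal; in practice it may reflect referral care and the stopped intervention. There is some questionnaire burden on distressed patients, and detection is not equalised between arms.
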